#### Figure 2 SCHEDULE 'B' Study Schematic

**Note**: Subjects who complete Study 812P306, but who rollover into Study 812P311 more than 7 days after their EOS Visit (812P306), subjects who were early terminated during Study 812P306, and *de novo* subjects will follow **SCHEDULE 'B'**. Screening is up to 28 days after obtaining informed consent at Visit 'S'. Subject taking any prohibited medications at screening (e.g., ADHD medications) should discontinue use (washout) at least 7-days prior to first dose of OLE SM. All subsequent study visits (2-22) will occur relative to the day/date of subject's first dose of SPN-812 (Day 1). Subjects who follow **SCHEDULE 'B'** will take first dose of OLE SM the morning of Visit. All subjects will initiate SPN-812 dosing at 200 mg once daily (QD) during the first 2 weeks of the study. At and after Visit 2, per the Investigator's discretion based on the subject's clinical response and tolerability, the dose of SPN-812 can be titrated up or tapered down in increments of 50 mg/day, 100 mg/day, 150 mg/day, or 200 mg/day per week to a target dose within the range between 200 and 600 mg/day. Subjects who complete the OLE Safety study should receive a follow-up phone call for safety 1 week after EOS.

# 3.2. Rationale for Study Design

An open-label uncontrolled study with safety as the primary endpoint is a standard design for evaluating the long-term safety of an investigational product in a clinical trial setting. The secondary efficacy endpoints for this study were selected to align with the efficacy endpoints used in the Phase 3 adult ADHD study 812P306 from which subjects would be enrolled.

A dose level range of 200 to 600 mg/day SPN-812 was selected based on the efficacy results from the Phase 2 adult and child phase 2 and Phase 3 pediatric studies, with flexible dosing permitted to align with real-world prescribing and treatment practices for ADHD.

# 3.3. Study Population

# 3.3.1. Number of Subjects

Up to 366 subjects will be enrolled. Subjects who completed Study 812P306 (a randomized, double-blind, placebo-controlled study of SPN-812 for the treatment of ADHD) will be eligible for enrollment into Study 812P311.

On a case-by-case basis, a subject who did not complete Study 812P306 (e.g., randomized, dosed SM and had at least one post-baseline AISRS assessment and then early terminated) may be allowed to screen and, if eligible, enroll in Study 812P311, **but only after receiving approval from the Site Investigator, Medical Monitor, and the Sponsor**.

*De novo* subjects (individuals who did not screen/enroll in Study 812P306) may screen and, if eligible, enroll in Study 812P311, but only after a "Note To File" has been submitted by the Sponsor to the IRB and approved. The clinical sites will be notified when the approval is granted.

# 3.3.2. INCLUSION/EXCLUSION CRITERIA 'A'

Use only for subjects who completed Study 812P306 and rolled over into Study 812P311 on **same day** as or **<5 days after their 812P306 EOS visit.** 

# 3.3.2.1. Inclusion Criteria 'A'

- 1. Is a male or female who completed Study 812P306 and opts/consents to participate in the study if approved by PI.
- 2. Continues to be medically healthy and with clinically normal laboratory profiles, vital signs, and electrocardiograms (ECGs), in the opinion of the Investigator, assessed at Visit 1.
- 3. Is able to read and understand the Informed Consent Form (ICF).
- 4. Has signed the ICF.

- 5. Is willing and able to attend study appointments within specified time windows.
- 6. Is a female of childbearing potential (FOCP) who is either sexually inactive (abstinent) or, if sexually active, agrees to use one of the following acceptable birth control methods beginning at least 30 days prior to the first dose of SM and throughout the study:
  - a. Simultaneous use of male condom and intra-uterine contraceptive device placed at least 4 weeks prior to first SM administration
  - b. Surgically sterile male partner
  - c. Simultaneous use of male condom and diaphragm with spermicide
  - d. Established hormonal contraceptive

Females are considered not to be of childbearing potential if they are either postmenopausal (amenorrhea for at least 2 years and serum follicle stimulating hormone [FSH] level of >40 IU/L) or permanently sterilized (e.g., bilateral tubal ligation, hysterectomy, bilateral oophorectomy for 6 months minimum prior to their Visit 1).

- 7. Is a male who:
  - Agrees to use 2 methods of contraception in combination if his female partner is of childbearing potential; this combination of contraceptive methods must be used from Visit 1 to ≥ 1 month after the last dose of SM, OR
  - b. Has been surgically sterilized prior to Visit 1.

# 3.3.2.2. Exclusion Criteria 'A'

- 1. Is currently participating in another clinical trial other than Study 812P306.
- Has any current psychiatric disorder per Diagnostic and Statistical Manual of Mental Disorders - 5th Edition (DSM-5) criteria other than ADHD with the following exceptions: ADHD is primary diagnoses with comorbidity/secondary diagnoses of major depression disorder (MDD), nicotine dependence, social anxiety disorder, generalized anxiety disorder, or phobias.
- 3. Current diagnosis of significant systemic disease and/or of a major psychiatric or neurological disorder, including history or family history of seizures or seizure-like disorders.
- 4. Current evidence of suicidality (suicidal thoughts or behaviors).
- 5. Female subjects who are pregnant, lactating and/or sexually active and not agreeing to use one of the acceptable birth control methods throughout the study.
- 6. Has a positive result on urine drug screen at Visit 1.
- 7. Use of prohibited concomitant medications including known CYP1A2 substrates (e.g., theophylline, melatonin) at the Visit 1 for the duration of the study.
- 8. Has a clinical laboratory value, vital sign value or ECG result at Visit 1 that is considered to be clinically significant in the opinion of the Investigator.

- 9. Has one or more clinical laboratory test values outside the reference range at Visit 1 that, in the opinion of the Investigator, are clinically significant, or any of the following (see Note below):
  - Serum creatinine > 1.5 times the upper limit of normal (ULN);
  - Serum total bilirubin > 1.5 times ULN;
  - Serum alanine aminotransferase or aspartate aminotransferase > 2 times ULN.
- 10. Has any of the following cardiology findings at Visit 1 (see Note below):
  - Abnormal ECG that is, in the Investigator's opinion, clinically significant;
  - PR interval > 220 ms;
  - QRS interval > 130 ms;
  - QTcF interval > 450 ms (for men) or > 470 ms (for women) (QT corrected using Fridericia's method);
  - Second- or third-degree atrioventricular block;
  - Any rhythm, other than sinus rhythm, that is interpreted by the Investigator to be clinically significant.
- 11. Any reason that, in the opinion of the Investigator, would prevent the subject from participating in the study.

Note: For subjects who follow **SCHEDULE** '**A**', with the approval from the investigator and the sponsor, repeat testing for clinical laboratory tests, vital signs, and ECG parameters is permitted one time within 1 week following Visit 1 prior to first dose for each test to determine eligibility.

# 3.3.3. INCLUSION/EXCLUSION CRITERIA 'B'

Use only for delayed rollover subjects (rolled over into Study 812P311 more than 7 days after their 812P306 EOS Visit), subjects who were early terminated during Study 812P306, and *de novo* subjects.

# 3.3.3.1. Inclusion Criteria 'B':

- 1. Is male or female, aged 18 to  $\leq$  65 years at screening.
- 2. Is able to read and understand the Informed Consent Form (ICF).
- 3. Written informed consent obtained from the subject (a signed ICF).
- 4. Weight within the normal or overweight ranges according to accepted values of the Body Mass Index (BMI) Chart (18.0 to 35.0 kg/m^2).
- 5. Is able to swallow capsules whole, without crushing, chewing or cutting.
- 6. Is willing and able to attend study appointments within the specified time windows.
- 7. Has a primary diagnosis of ADHD according to the DSM-5 classification, with diagnosis made at least 6 months prior to screening and confirmed with Structured Clinical Interview for DSM-5 Clinical Trials version (SCID-5-CT; *de novo* subjects).
- 8. Has an AISRS total score of  $\geq$  24 at the screening (Visit 'S').
- 9. Has a CGI-S score of  $\geq$  4 (mildly ill or worse) at the screening (Visit 'S').

- 10. Females of childbearing potential (FOCP) must be either sexually inactive (abstinent) or, if sexually active, must agree to use one of the following acceptable birth control methods beginning at least 28 days prior to the first dose of SM and throughout the study:
  - a. Simultaneous use of male condom and intra-uterine contraceptive device placed at least 4 weeks prior to first SM administration
  - b. Surgically sterile male partner
  - c. Simultaneous use of male condom and diaphragm with spermicide
  - d. Established hormonal contraceptive

Females are considered not to be of childbearing potential if they are either postmenopausal (amenorrhea for at least 2 years and serum follicle stimulating hormone [FSH] level of >40 IU/L) or permanently sterilized (e.g., bilateral tubal ligation, hysterectomy, bilateral oophorectomy for 6 months minimum prior to screening).

- 11. Males must:
  - a. Use 2 methods of contraception in combination if his female partner is of childbearing potential; this combination of contraceptive methods must be used from Visit 1 (baseline) to ≥ 1 month after the last dose of SM; or
  - b. Have been surgically sterilized prior to the Screening Visit.

# 3.3.3.2. Exclusion Criteria 'B'

- 1. Is currently participating in another clinical trial or has participated in a clinical trial within 60 days prior to screening, with the exception of Study 812P306.
- 2. Is a member of the study personnel or of their immediate families, or is a subordinate (or immediate family member of a subordinate) to any of the study personnel.
- 3. Female subjects who are pregnant, lactating and/or sexually active and not agreeing to use one of the acceptable birth control methods throughout the study.
- 4. Has a history of severe drug allergy or hypersensitivity, or known hypersensitivity, to the study medication.
- 5. Has a history of moderate or severe head trauma or other neurological disorder or systemic medical disease that, in the Investigator's opinion, is likely to affect central nervous system functioning. This would include subjects with:
  - a. A current diagnosis of a major neurological disorder; or
  - b. Seizures, seizure disorder or seizure-like events; or a history of seizure disorder within the immediate family (siblings, parents); or Encephalopathy
- 6. Has any history of schizophrenia, schizoaffective disorder, bipolar disorder, borderline personality disorder, antisocial personality disorder, narcissistic personality disorder, autism, post-traumatic stress disorder or obsessive-compulsive disorder.
- 7. Has any current psychiatric disorder (per DSM-5 criteria) other than ADHD with the following exceptions: ADHD is primary diagnoses with comorbidity/secondary

diagnoses of major depression disorder (MDD), nicotine dependence, social anxiety disorder, generalized anxiety disorder, or phobias, and subject is not receiving pharmacological treatment for the comorbidity/secondary diagnoses (e.g., antidepressant for MDD) at time of screening nor for the duration of study.

- 8. Has organic mental disorders, or mental disorders due to a general medical condition (per DSM-5 criteria).
- 9. Has a current diagnosis or history of substance use disorder including alcohol use disorder (excluding nicotine and caffeine) (per DSM-5 criteria) within the 12 months prior to screening; or is assessed by the Investigator as having regularly consumed alcohol exceeding 21 units for males and 14 units for females per week (1 unit equals 340 mL of beer, 115 mL of wine, or 43 mL of spirits) within the 12 months prior to screening.
- 10. Is currently using, or has a positive result on the drug screening at the Screening Visit for drugs of abuse (alcohol, opiates, methadone, cocaine, methamphetamine [including ecstasy], phencyclidine, propoxyphene, methylphenidate, barbiturates, and benzodiazepines). If subject's serum drug screen for ethanol is positive at screening (Visit 'S') and the investigator determines subject does not have alcohol use disorder, then the subject may have a repeat serum drug screen for ethanol performed before Visit 1 within the allotted screening period (results must be received prior to Visit 1). If second serum drug screen for ethanol is positive, subject is excluded from participating in the study, however, if second serum drug screen for ethanol is negative, subject may proceed to Visit 1.
- 11. Is a (known or self-identified) current habitual/chronic cannabis user (medicinal or recreational); or
  - Has a positive urine drug screen for cannabis at screening (Visit 'S') and is considered, per the Investigator's judgement, to be a habitual/chronic cannabis user; or
  - Has a positive urine drug screen for cannabis at both the screening (Visit 'S') and follow-up drug screen (Visit 1), even though the subject is not considered, per the Investigator's judgement, to be a habitual/chronic cannabis user.

Note: Subjects who have a positive urine drug screen for cannabis at screening (Visit 'S') but who are not considered, per the Investigator's judgement, to be a habitual/chronic cannabis user may, with Sponsor approval, undergo an additional urine drug screen at least 4 weeks after the initial urine drug screen at Visit 1 prior to randomization. Subjects must agree to refrain from cannabis use throughout study.

12. Has treatment-resistant ADHD based on a history of receipt of >2 approved ADHD medications that failed to adequately improve the subject's symptoms, with the

exception of subjects who completed Study 812P306. A subject who is naïve to ADHD treatment is not excluded from study participation.

- 13. Has any other disorder for which its treatment takes priority over treatment of ADHD or is likely to interfere with study treatment, impair treatment compliance, or interfere with interpretation of study results.
- 14. Has a history of cancer, other than basal cell or Stage 1 squamous cell carcinoma of the skin that has not been in remission for > 5 years prior to the first dose of SM.
- 15. Has or has had one or more of the following conditions considered clinically significant/relevant by the Investigator in the context of the study:
  - cardiovascular disease
  - congestive heart failure
  - cardiac hypertrophy
  - arrhythmia
  - bradycardia (pulse < 50 bpm)

  - tachycardia (pulse > 100 bpm)
  - respiratory disease
  - hepatic impairment or renal insufficiency
  - metabolic disorder
  - endocrine disorder
  - gastrointestinal disorder
  - hematological disorder
  - infectious disorder
  - any clinically significant immunological condition
  - dermatological disorder
- 16. Exhibits clinically significant abnormal vital signs at screening (see Note below).
- 17. Has one or more screening clinical laboratory test values outside the reference range that, in the opinion of the Investigator, are clinically significant, or any of the following (see Note below):
  - Serum creatinine > 1.5 × the upper limit of normal (ULN);
  - Serum total bilirubin > 1.5 × ULN;
  - Serum alanine aminotransferase or aspartate aminotransferase > 2 × ULN.
- 18. Has any of the following cardiology findings at screening (see Note below):
  - Abnormal ECG that is, in the Investigator's opinion, clinically significant;
  - PR interval > 220 ms;
  - QRS interval > 130 ms;
  - QTcF interval > 450 ms (for men) or > 470 ms (for women) (QT corrected using Fridericia's method);
  - Second- or third-degree atrioventricular block;
  - Any rhythm, other than sinus rhythm, that is interpreted by the Investigator to be clinically significant.

- 19. Has any disease or medication that could, in the Investigator's opinion, interfere with the assessments of safety, tolerability, or efficacy, or interfere with study conduct or interpretation of results.
- 20. Evidence of infection with hepatitis B or C, or human immunodeficiency virus (HIV)-1 or HIV-2, as determined by results of testing at screening.
- 21. Lost or donated more than 450 mL of blood during the 30 days prior to screening.
- 22. Use of any investigational drug or prohibited concomitant medications including known CYP1A2 substrates (e.g., theophylline, melatonin) within 30 days or 5 half-lives prior to Visit 1 (baseline) (whichever is longer) during the screening period or anticipated for the duration of the study.
- 23. History of unexplained loss of consciousness, unexplained syncope, unexplained irregular heartbeats or palpitations or near drowning with hospital admission.
- 24. Has attempted suicide within the 6 months prior to screening, or is at significant risk of suicide, either in the opinion of the Investigator or defined as a "yes" to suicidal ideation questions 4 or 5 or answering "yes" to suicidal behavior on the Columbia-Suicide Severity Rating Scale (C-SSRS) within the 6 months prior to screening.
- 25. In the Investigator's opinion, is unlikely to comply with the protocol or is unsuitable for any other reason.

Note: For subjects who follow **SCHEDULE** '**B**', with the approval from the investigator, medical monitor and the sponsor, repeat testing for clinical laboratory tests, vital signs, and ECG parameters is permitted one time for each test, at the discretion of the Investigator, as long as the repeat test result is available within the 28-day screening period (prior to first study dose) to determine eligibility.

### 3.4. Completion of Study and Discontinuation of Subjects

Subjects will be considered to have completed the study if they complete all visits up to and including Visit 22 (EOS).

If SPN-812 is not approved for Adults at the time of Visit 22, subjects may choose to continue in the study; repeating Visit 21 procedures every 8 weeks (including FPC in 4 weeks after each subsequent study visit) until SPN-812 becomes approved and commercially available for Adults.

Subjects who are enrolled and dosed with SM, but who withdraw or are withdrawn from participation in the study by the Investigator before he/she finishes the study (i.e., prior to Visit 22), should complete an early termination (ET) Visit. Procedures listed for the EOS visit should be completed at the ET Visit.

All reasons for screen failure will be recorded.

The Investigator(s) or subjects themselves may stop SM treatment at any time for safety or personal reasons. A subject is free to withdraw from the study at any time for any reason without prejudice to their future medical care by the physician or at the institution.

This document is confidential. It contains proprietary information of Supernus® Pharmaceuticals, Inc. Any viewing or disclosure of such information that is not authorized in writing by the Sponsor is strictly prohibited. Such information may be used solely for the purpose of reviewing or performing this study.

The Sponsor may also withdraw subject participation in the study without consent for any reason, but is in the best interest of subject safety. The withdrawal of a subject from the study should be discussed where possible with the Medical Monitor and Clinical Research Associate (CRA) before the subject stops SM. Subjects removed from the study for any reason will not be replaced.

Reasons for a subject's early discontinuation may include:

- Subject lost to follow-up
- Subject's withdrawal of consent
- Investigator ended subject's participation in study
- Other

The primary reason for the subject's early discontinuation must be recorded in the subject's medical record and on the electronic case report form (eCRF). If a subject is withdrawn for more than one reason, each reason should be documented in the source document and the most medically significant reason should be entered on the eCRF.

# 4. Study Treatment

### 4.1. Study Medication Identity, Packaging and Labeling

Study medication is supplied as capsules that contain 100 mg, 150 mg and 200 mg of SPN-812, packaged in bottles. Each bottle will be labeled with the protocol number and subject ID, at a minimum.

### 4.2. Study Medication Administration

Study medication will be administered orally once daily (QD) as intact capsules, with or without food. The daily dose should be taken in the morning. Splitting the daily dose (e.g., taking part of the daily dose in the morning and the remainder of the daily dose in the evening) is not permitted. Confirm that subject is taking daily dose in the morning; if subject reports that he/she is taking daily dose later in the day (e.g., evening) without prior Site Investigator or Sponsor approval, the medical monitor must be informed immediately. The medical monitor must then inform the Sponsor.

Subjects who follow:

- SCHEDULE 'A' will take first dose of OLE SM the morning after Visit 1 at home.
- SCHEDULE 'B' will take first dose of OLE SM the day of Visit 1 at clinic.

All subjects will initiate SPN-812 dosing at 200 mg/day during first 2 weeks of the study. At and after Visit 2, per the Investigator's discretion based on the subject's clinical response and tolerability, the dose of SPN-812 can be titrated up or tapered down in increments of 50 mg/day, 100 mg/day, 150 mg/day, or 200 mg/day per week to a target dose within the range between 200 and 600 mg/day.

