For subjects who follow **SCHEDULE** '**A**', the total study duration per subject from Visit 1 to Visit 22/EOS will be ~156 weeks (3 years) or until SPN-812 becomes approved and commercially available for Adults.

For subjects who follow **SCHEDULE** '**B**', the total study duration per subject is up to 160 weeks, including screening (up to 4 weeks) and from Visit 1 to Visit 22/EOS (up to ~156 weeks [3 years]), or until SPN-812 becomes approved and commercially available for Adults.

Details of each study visit are provided in Section 5.

[figure not shown]
Unscheduled visits may be conducted at the discretion of the Investigator for safety reasons or to dispense additional SM throughout the study. AEs, concomitant medications and caffeine use will be assessed at all scheduled and unscheduled visits.

**Note**: Subjects who complete Study 812P306 and rollover into Study 812P311 on the same day as or ≤ 7 days after their 812P306 EOS visit will follow **SCHEDULE** '**A**. The assessments collected during 812P306 EOS Visit will serve as assessments for 812P311 Visit 1 (Day -1). All subsequent study visits (2-22) will occur relative to the day/date of subject's first dose of SPN-812 (Day 1). Subjects who follow **SCHEDULE** '**A**' will take first dose of OLE SM the morning after Visit 1. All subjects will initiate SPN-812 dosing at 200 mg once daily (QD) during the first 2 weeks of the study. At and after Visit 2, per the Investigator's discretion based on the subject's clinical response and tolerability, the dose of SPN-812 can be titrated up or tapered down in increments of 50 mg/day, 100 mg/day, 150 mg/day, or 200 mg/day per week to a target dose within the range between 200 and 600 mg/day. Subjects who complete the OLE Safety study should receive a follow-up phone call for safety 1 week after EOS.

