### 5.1.1. Study Initiation

#### 5.1.1.1. SCHEDULE 'A' ['Same day/Short Delayed (≤7 day)' Rollover Subjects]:

#### 5.1.1.1.1. Visit 1 – Initial Study Visit

The following assessments will be conducted:

- Review Inclusion/exclusion criteria
- ICF signed
- Social, medical, psychiatric, family psychiatric, and neurological histories
- Demographics
- Smoking and alcohol consumption use/history
- Physical examination
- Blood sample for:
  - FSH (post-menopausal females only)
  - Chemistry and hematology
- Urine sample for:
  - o Urinalysis
  - Urine pregnancy test (FOCP only)
  - Point of Care Urine Drug Screen Test 1/Test 2 (see Table 3)
- Vital signs (includes orthostatic blood pressure/heart rate) and weight
- Perform ECG
- C-SSRS ('Since Last Visit' version)
- AISRS, CGI-I, CGI-S, GAD-7, BRIEF-A, SDQ and AAQoL
- Review concomitant medications and Caffeine use
- Review adverse events (events occurring before first dose of SPN-812 should be recorded as medical history; events occurring after first dose of SPN-812 should be recorded as an AE)
- Dispense Study Medication; subject should take first dose of SPN-812 at home in the morning the next day after Visit 1.

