#### 6.5. Clinical Measurements

#### 6.5.1. Clinical Safety Laboratory Assessments

With the exception of urine pregnancy tests and urine drug screen tests, clinical laboratory tests are performed by a central laboratory as specified in the reference binder.

Details for collecting, handling, and shipping samples (including shipment addresses) are detailed in a separate clinical laboratory manual. The Schedule of Events and Assessments (Table 1 [SCHEDULE 'A'] or Table 2 [SCHEDULE 'B']) shows the time points at which blood and urine samples are collected. Table 3 presents the clinical laboratory tests to be performed.

Category	Parameters						
Serology	Human immunodeficiency virus (HIV)-1, HIV-2, hepatitis B, hepatitis C; Visit 'S', SCHEDULE 'B' only						
Hematology	Red blood cell count, hemoglobin, hematocrit, platelet count, and WBC count with differential						
Chemistry	Electrolytes: Chloride, phosphate, potassium, sodium						
	Liver function tests : Alkaline phosphatase, aspartate aminotransferase, alanine aminotransferase, total bilirubin, direct bilirubin						
	Renal function parameters: Blood urea nitrogen, creatinine						
	Other: Glucose, Ca +2 , albumin, total protein, bicarbonate						
	FSH: Post-menopausal females only						
Urinalysis	Macroscopic examination a , pH, specific gravity, protein, glucose, ketone, occult blood, WBC, nitrites, bilirubin, urobilinogen						
Serum Drug Screen	Ethanol; Visit 'S', SCHEDULE 'B' only						
'Standard' Urine Drug Screen (UDS)	amphetamines, barbiturates, benzodiazepines, buprenorphine, cocaine, ecstasy, methadone, methamphetamine, opiates, oxycodone, phencyclidine, propoxyphene, tricyclic antidepressant, THC (cannabinoids); Visit 'S', SCHEDULE 'B' only						
Point of Care Urine Drug Screen	Test 1 : amphetamines, barbiturates, benzodiazepines, buprenorphine, cocaine, ecstasy, methadone, methamphetamine, opiates, oxycodone, phencyclidine, propoxyphene, tricyclic antidepressant, THC (cannabinoids).						
	Test 2: methylphenidate						
On site Urine Pregnancy Test (at all study visits)	FOCP only						
Home Urine Pregnancy Test (in between study visits following study visit 3)	FOCP only (dispense home pregnancy kit at Study Visits 3 thru 21)						

Table 3	Clinical Laboratory Tests
---------	---------------------------

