# 6.5.4. Electrocardiograms (ECGs)

A 12-lead ECG will be obtained at the time points shown in the Schedule of Events and Assessments (Table 1 [SCHEDULE 'A'] or Table 2 [SCHEDULE 'B']). Additional ECGs may be performed at other times if deemed necessary by the Investigator.

The ECG will be recorded while the subject is resting in a supine position for at least 10 minutes. The ECG will electronically measure the PR, QRS, QT, and QTc intervals, and heart rate. All ECG tracings will be reviewed within 24 hours by the Investigator or qualified Sub-investigator. PR intervals will be determined for each of these ECGs from a single reading. Invalid measurements will be repeated. QTc will be reported as QTcF (QT corrected using Fridericia's method).

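### Same-day Schedule A rollovers can take the first dose before the central-laboratory results that decide exclusions A8 and A9 are known, and the repeat-test Note conflicts with the fixed next-morning dose

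*Protocol*

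**What the plan says.** **Dosing.** Protocol Section 4.2 states that "SCHEDULE 'A' will take first dose of OLE SM the morning after Visit 1 at home". The Visit 1 procedures in Section 5.1.1.1.1 end with "Dispense Study Medication; subject should take first dose of SPN-812 at home in the morning the next day after Visit 1". The Figure 1 note in Section 3.1 says the same, and Table 1 puts Visit 1 at Day -1 and the first dose at Day 1, with no window on either.

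**Source of Visit 1 data.** Schedule A covers rollover from the same day up to 7 days after the 812P306 EOS visit. Sections 3.1 and 5.1 let the EOS assessments stand in for those of Visit 1.

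**Eligibility.** Section 3.3.2.2 excludes a subject who "Has one or more clinical laboratory test values outside the reference range at Visit 1" that the investigator finds clinically significant, or who exceeds set limits for creatinine, bilirubin or ALT/AST (A9). A8 covers clinically significant laboratory, vital sign or ECG results, and A10 covers ECG findings.

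**Repeats.** The Note under the same criteria says that repeat testing "is permitted one time within 1 week following Visit 1 prior to first dose for each test to determine eligibility".

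**When results arrive.** Section 6.5.1 says that, apart from urine pregnancy and urine drug tests, "clinical laboratory tests are performed by a central laboratory as specified in the reference binder". It gives no turnaround time. For ECGs, Section 6.5.4 says "All ECG tracings will be reviewed within 24 hours by the Investigator or qualified Sub-investigator".

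**The concern.** An exclusion based on a laboratory value protects a subject only if the value is known before dosing. On the day of a same-day rollover, blood is drawn for a central laboratory, drug is handed out, and the subject is told to take it at home the next morning. If the creatinine, bilirubin or transaminase result arrives later, a subject who meets A9 has already been dosed and belongs to the Safety Population. Same-day entry is a main route, since Section 3.1 arranges for interest to be established before the end of 812P306 so that enrollment can be immediate.

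The repeat-test Note raises the same question. A week is allowed for a repeat that must come before the first dose, but the dosing passages place that dose on the first morning of the week. A site following Sections 4.2 and 5.1.1.1.1 literally would have little use of the window.

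**Working it through.** The plan gives no figure to reproduce. The check is day arithmetic on the stated schedule.

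**Inputs**
- Visit 1 = Day -1; first dose = morning of Day 1 (Table 1, Sections 3.1, 4.2 and 5.1.1.1.1). This is one overnight interval, about 1 day.
- Rollover lag L after 812P306 EOS = 0 to 7 days (Sections 3.1 and 5.1).
- Repeat window = 7 days after Visit 1, before first dose (Note to Criteria A).
- Laboratory turnaround T is not stated. The range 1 to 3 days is an assumption.

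**Step 1: share of the repeat window before dosing.** 1 / 7 = 14%. The other 6 days fall after the scheduled first dose.

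**Step 2: time from EOS draw to first dose.** Interval = L + 1 day.
- Same-day rollover: 0 + 1 = about 1 day.
- Seven-day lag: 7 + 1 = about 8 days.

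**Step 3: are first results back?** They are late if T > L + 1, borderline if T is about L + 1, and in time if T < L + 1.

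| Assumed T | L = 0 | L = 1 | L = 2 | L = 3 to 7 |
|---|---|---|---|---|
| 1 day | borderline | in time | in time | in time |
| 2 days | late | borderline | in time | in time |
| 3 days | late | late | borderline | in time |

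**Step 4: a repeat for a same-day rollover.** If the second sample is drawn on the day the first result arrives, the second result comes about 2T after Visit 1. That is 2 × 1 = 2 days to 2 × 3 = 6 days. It fits the Note's 7 days but not the 1 day before the scheduled dose.

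**Step 5: passages side by side.** Sections 3.1 (Figure 1 note), 4.2 and 5.1.1.1.1 and Table 1 contain no step that holds the dose for a pending result or an approved repeat. For Schedule B, the Note in Section 3.3.3.2 does require the repeat result to be available in the 28-day screening period before first dose. The two Schedule A Notes also differ on approval: the synopsis names the investigator, medical monitor and sponsor, while Section 3.3.2.2 names only the investigator and sponsor.

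**Step 6: next scheduled check.** Visit 2 (Section 5.1.2) has neither chemistry nor ECG. Both next appear at Visit 3, Day 29 (Section 5.1.3).

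**The case against.** A reader might infer that exclusions A8 to A10 cannot work at all for Schedule A. The documents do not support that.

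- **Delayed rollovers.** They use EOS results, which may be back before dosing (Step 3). The number of same-day rollovers is not known.
- **Vital signs and ECG.** Vital signs are known at the visit. ECG intervals are measured electronically, and 24 hours is the upper limit for site review. A review that uses the full limit could end after a morning dose, but nothing requires that.
- **Turnaround.** It may be set in the reference binder or laboratory manual, which are not available here. Late results are therefore conditional on the assumed range.
- **The Note.** One week is a maximum, and the requirement that the repeat come before first dose can be read as deferring the dose when a repeat is approved. Later visits are timed from first dose, so deferral would not disturb them. This reading is reasonable, but no dosing passage states it and the drug is already at home.
- **General safeguards.** Treatment can be stopped for safety at any time (Section 3.4), unscheduled tests are allowed (Section 5.1.7), and deviations are notified (Section 5.1) and summarized (SAP Section 2.2). Day 29 is therefore only the next scheduled check. None of these addresses a Visit 1 result that arrives after dosing.

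A reader might also infer that the primary safety tables are materially contaminated. That goes too far. Findings before first dose are recorded as medical history, and the safety baseline is the last value before dosing (SAP Section 3.2). The potentially clinically significant (PCS) tables count only post-baseline values, and their liver limits are above those of A9: ALT/AST 3 against 2 times ULN, and bilirubin 2 against 1.5 times ULN. An abnormality that persisted beyond a PCS limit would still be counted.

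**Conclusion.** The point holds in a limited form. For same-day Schedule A rollovers, the protocol does not ensure that the laboratory results behind A9 and the laboratory part of A8 are known before the first dose. How often they would be late depends on turnaround: borderline at 1 day, late at 2 to 3 days. The conflict between the repeat-test Note and the next-morning dose does not depend on turnaround, since about 1 of 7 days precedes the dose and no dosing passage mentions a hold.

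This is more than missing detail, because following the dosing passages as written can expose a subject before a safety exclusion is resolved. The expected effect on the summary tables is small. The differing approvers are a separate editorial inconsistency and add nothing to the severity. Should-fix, moderate confidence.

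**What to change.** Reconcile Section 3.1 (Figure 1 note), Section 4.2, Section 5.1.1.1.1 and Table 1 with exclusions A8 and A9, both versions of the Note to Criteria A (synopsis and Section 3.3.2.2) and Section 6.5.1. Result review, the repeat-test window and first dose should follow one order, stated the same way in each place. Which order is right is the sponsor's clinical decision.

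Name the same approvers of repeat tests in the synopsis Note and the Section 3.3.2.2 Note.

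Optionally, identify in the deviation or laboratory listings already planned in SAP Section 5.2 any Schedule A subject dosed with a Visit 1 value that met A8 to A10.

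The cost is a protocol wording amendment and, if the option is taken, one flag in an existing listing. No visits, tests or subjects are added. Depending on the order chosen, some subjects might have a few days between Visit 1 and Day 1. Later visits are counted from first dose and would keep their spacing.
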